5.2.2 Exclusion criteria

Candidates for this clinical trial must not fall under any one of the following exclusion criteria:

- 52 -

silicon, or polymeric materials.

- (17) Patient has had a cerebrovascular accident or transient ischemic attack within 6 months prior to the study procedure. Except cases with an event associated with AS.
- (18) Patient with poorly controlled blood pressure.
- (19) Patient has serum albumin < 3.0 g/dL or body mass index (BMI) < 18.
- (20) Patient has uncontrollable diabetes mellitus.
- (21) Patient has active bacterial endocarditis or other active infection.
- (22) Patient has life expectancy < 12 months due to pre-operative non-cardiac comorbidity (e.g., cancer, chronic liver disease).
- (23) Currently participating in an investigational drug or another device study. [Note: Trials requiring extended follow-up for products that were investigational, but have since become commercially available, are not considered investigational trials.]
- (24) Cardiovascular surgeons and cardiologists concluded that the patient is inappropriate for participating in this trial.

<TF approach>

- (25) Patient has significant tortuous aorta, diseases including abdominal aortic or thoracic aneurysm, or significant atheroma in the femoral artery or iliac artery that would prevent from proper placement of delivery system.
- (26) Patient has iliofemoral vessel characteristics that would preclude safe placement of 14F or 16F introducer sheath such as severe obstructive calcification and severe tortuosity, or minimum average vessel size less than 5.5 mm (6.0 mm for 16F introducer sheath).

<Rationales for the setting>

The exclusion criteria for this clinical trial were set up in reference to the inclusion criteria for a US clinical study of the study device PARTNER II study, Japanese clinical studies of previous generation SAPIEN XT PREVAIL JAPAN study (EW-P-001) and PREVAIL-20 JAPAN study (EW-P-002), and advanced medical care that evaluated TAVI with SAPIEN and SAPIEN XT in chronic dialysis patients. The rationales for the setting of individual exclusion criteria are as shown in the followings:

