9.2.2 Secondary efficacy endpoints

- Device success: 30 days after procedure
- Length of post-procedural hospitalization/ICU stay: At discharge
- NYHA classification: Post-procedure 30 days, 6 months, 1 year, and 2 to 5 years annually
- Six-minute walk test: Post-procedure 30 days and 1 year
- Quality of life (QOL) (EuroQOL, short form 12-item health survey [SF-12]): Post-procedure 30 days, 6 months, 1 year, and 2 to 5 years annually

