15.1.2 Statistical analysis plan and statistical method

Mortality at 1 year post-procedure, the primary endpoint, will be analyzed in the AT analysis set to verify the non-inferiority of EWJ-003 therapy to the standard therapy. The non-inferiority test will be performed

- 104 -

made and reasons for the changes, and the Statistical Analysis Plan should be revised.

All deviations from the Statistical Analysis Plan should be described in the Study Report.

- 106 -

using one-sided Fisher's exact test, and at one-sided significant level of 0.05 if the 95% CI upper limit for the mortality at 1 year post-procedure is lower than the PG (45%), non-inferiority of EWJ-003 therapy to the standard therapy would be verified.

No statistical tests will be conducted for the secondary endpoints, but evaluate by descriptive statistics. The secondary valve performance endpoints based on the echocardiographic evaluation will be analyzed in the VI analysis set, and other secondary endpoints. Other data including subject background and baseline characteristics, and procedure information, etc. will be summarized by descriptive statistics.

All statistical analyses will be performed for, in addition to the entire analysis sets, each approach of TF, TA, and TAO. For continuous variables, the number of measurements, mean, standard deviation, median, quartile, minimum, maximum, and 95% CI of the mean will be calculated. On the other hand, for categorical variables, the number of samples (n), percentage (%), and for binary variables 95% CI will be calculated. For the primary endpoint and secondary safety and efficacy endpoints, the cumulative incidence will be calculated by Kaplan-Meier estimates as needed.

The detailed statistical analysis plan and statistical method are included in the Statistical Analysis Plan.

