Device deficiency	A device deficiency is defined as the failure of a device to meet its quality, safety, and performance specifications, such as damage and/or malfunctioning, regardless of being associated with the design, supply, storage, or used.	J-GCP
Valve malposition	Valve malposition includes moved valve, valve embolism, and implantation at an unintended site. For definition of events, see respective section.	VARC-2

Term	Definition	Reference/rationale
Moved valve	After a prosthetic valve was placed in an appropriate position, the valve moved upward or downward in the aortic annulus from the implanted site, with or without a causal relationship to the study procedure.	VARC-2
Valve embolism	The prosthetic valve moved during or after implantation, and no longer stay in the annulus.	VARC-2
Implantation at an unintended site	A prosthetic valve being persistently implanted at the site other than the aortic root.	VARC-2
Device success	
No operative death (death within 30 days post-procedure or death during hospital stay), the investigational valve was implanted at an appropriate anatomical position, and all intended performance of the investigational valve as shown in the followings were achieved.
 
 No prosthetic valve - patient mismatch Mean pressure gradient < 20 mmHg or maximum aortic flow velocity < 3 m/s No ≥ moderate aortic valve regurgitation 	VARC-2
Dry weight	The body fluid volume is proper, without excessive decrease in blood pressure during dialysis, and body weight with less burden on the cardiovascular system in a long-term basis.	Guidelines for evaluation and treatment of cardiovascular complication in hemodialysis patients
Dialysis conditions	
The dialysis conditions are as shown below:
 
 Number of dialysis per week (times/week) Duration of dialysis (hours) Blood flow (mL) Quantity of dialysate flow (mL) Removal method (filtration or diffusion) Dialyzer membrane type and membrane area With or without High Performance Membrane (HPM) dialyzer 	Guidelines for maintenance hemodialysis: Blood prescription

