Paravalvular regurgitation	
All blood leakages around the prosthetic valve associated with the gap between the prosthetic valve and native annulus.
 
Paravalvular regurgitation can be classified as follows:
 
Total regurgitation: Moderate to severe paravalvular dysfunction clearly observed by echocardiography.
 
Mild regurgitation: Paravalvular regurgitation classified as aortic valve regurgitation < 3+ and not requiring surgical intervention.
 
Severe regurgitation: Aortic valve regurgitation $\geq 3+$ and requiring surgical intervention.
 
(also see "Non-structural dysfunction")
	STS/AATS								
Pre-procedural complication	Defined as any complication developed before the start of the study procedure and the symptoms sustained or under treatment at the start of the study procedure.									

Term	Definition	Reference/rationale												
Prosthesis-patient mismatch (PPM)	
Prosthesis-patient mismatch (PPM) is an index to show a relationship between the implanted prosthetic valve and cardiac output originally required for the subject. When the aortic flow velocity coefficient by continuous wave Doppler method is normal (> 0.35), but $EOAi \leq 0.85$ ($BMI < 30$), it is regarded as hemodynamically significant prosthesis-patient mismatch.
 
  
 	Not significant	Moderate	Severe	
   
 $EOAi$ (cm^2/m^2)	> 0.85	$0.85 - 0.65$	< 0.65	
 
 $BMI \geq 30$ (kg/cm^2)	> 0.70	$0.90 - 0.60$	< 0.60	
  
		Not significant	Moderate	Severe	$EOAi$ (cm^2/m^2)	> 0.85	$0.85 - 0.65$	< 0.65	$BMI \geq 30$ (kg/cm^2)	> 0.70	$0.90 - 0.60$	< 0.60	VARC-2
	Not significant	Moderate	Severe											
$EOAi$ (cm^2/m^2)	> 0.85	$0.85 - 0.65$	< 0.65											
$BMI \geq 30$ (kg/cm^2)	> 0.70	$0.90 - 0.60$	< 0.60											
Re-hospitalization	
Re-hospitalized due to AS symptoms and/or post-procedural complication.
 
If the post-procedural hospital stay exceeds 30 days, in-hospital Day 31 is statistically regarded as re-hospitalization.
													
Re-intervention	All interventions including repair, correction, or replacement of the already operated valve.	STS/AATS												

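### For BMI of 30 or more, the glossary grades an indexed orifice area above 0.70 and up to 0.90 as both no significant mismatch and moderate mismatch, which can leave device success ambiguous

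*Combined protocol and SAP*

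**What the plan says.** Section 9.2.2 lists "Device success: 30 days after procedure" among the secondary efficacy endpoints. The Section 30 Glossary entry for device success requires no operative death, correct anatomical position, and that "all intended performance of the investigational valve as shown in the followings were achieved". The first item on that performance list is "No prosthetic valve - patient mismatch". The other two are a gradient or velocity limit and no regurgitation of moderate grade or worse. The entry names no grade of mismatch.

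The glossary entry for prosthesis-patient mismatch (PPM) has a sentence and a table. The sentence says that when the velocity coefficient is normal (> 0.35) but EOAi is ≤ 0.85, with BMI < 30, "it is regarded as hemodynamically significant prosthesis-patient mismatch". It gives no limit for BMI ≥ 30. The table has three columns (not significant, moderate, severe) and two rows:

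- general EOAi row: "> 0.85 $0.85 - 0.65$ < 0.65"
- BMI ≥ 30 row: "> 0.70 $0.90 - 0.60$ < 0.60"

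The BMI ≥ 30 row prints its BMI unit as kg/cm², whereas Section 10.2.1 computes BMI as kg/m².

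**The concern.** A grading table that feeds a binary endpoint should give one grade per value. The general row does: its classes meet at 0.85 and at 0.65. The BMI ≥ 30 row does not, because its moderate class begins at 0.90 while its not-significant class begins just above 0.70.

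The 0.90 also points the wrong way within its own row. The other two limits are relaxed for the higher BMI group, but 0.90 is stricter than the general 0.85. Read literally, an EOAi of 0.88 is not significant in a subject with BMI below 30, and both not significant and moderate in a subject with BMI of 30 or more.

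At stake is the device success percentage, which Section 15.1.2 reports with a 95% CI as a binary variable. The synopsis and Section 27 show main-set enrolment as closed. Unless a rule is written down elsewhere, the reading of this row could be settled when the values are already available.

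**Working it through.** **Inputs.** The two table rows, the PPM sentence and the device success entry are from Section 30. The sample size of 30 is from Section 4.3. The BSA and BMI formulas are from Section 10.2.1. Section 5.2.2 sets only a lower BMI limit ("Patient has serum albumin < 3.0 g/dL or body mass index (BMI) < 18"), so subjects with BMI ≥ 30 can enrol. There is no sample size, power or alpha figure to reproduce for this point.

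**Step 1: grade every value.** Each row was applied to EOAi from 0.40 to 1.20 in steps of 0.01.

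| Row | Values with two grades | Values with no grade |
|---|---|---|
| General (> 0.85; 0.85–0.65; < 0.65) | 0 | 0 |
| BMI ≥ 30 as printed (> 0.70; 0.90–0.60; < 0.60) | 20 (0.71 to 0.90) | 0 |
| BMI ≥ 30, moderate set to 0.70–0.60 | 0 | 0 |
| BMI ≥ 30, not significant set to > 0.90 | 0 | 0 |

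The overlap is 0.70 < EOAi ≤ 0.90. A value of exactly 0.70 is moderate only, and a value above 0.90 is not significant only. The two repairs grade the whole band in opposite ways.

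**Step 2: compare the limits by direction.** Not significant: 0.70 against 0.85, lower. Severe: 0.60 against 0.65, lower. Upper end of moderate: 0.90 against 0.85, higher. Only the 0.90 breaks the pattern.

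**Step 3: express the band as valve area.** For an illustrative subject of 160 cm and 77 kg:

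- BMI = 77 / 1.60² = 30.1 kg/m²
- BSA = 0.007184 × 77^0.425 × 160^0.725 = 1.803 m²
- 0.70 × 1.803 = 1.26 cm² and 0.90 × 1.803 = 1.62 cm²

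For this subject, any EOA above 1.26 and up to 1.62 cm² is graded twice.

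**Step 4: effect on the rate.** With 30 subjects evaluable, each affected subject who meets every other component moves device success by 1/30 = 3.3 percentage points. As an illustration, assume 27 successes when affected subjects count as successes, and recount them as failures (exact 95% CIs):

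- 0 affected: 27/30 = 90.0% (73.5 to 97.9)
- 1 affected: 26/30 = 86.7% (69.3 to 96.2)
- 2 affected: 25/30 = 83.3% (65.3 to 94.4)
- 3 affected: 24/30 = 80.0% (61.4 to 92.3)

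**Step 5: how many subjects.** The protocol gives no BMI distribution. If 2% to 10% had BMI ≥ 30 (assumption), the expected number with BMI ≥ 30 is 30 × 0.02 = 0.6 to 30 × 0.10 = 3, and the chance of at least one is 1 − 0.98^30 = 45% to 1 − 0.90^30 = 96%. These figures count all subjects with BMI ≥ 30. To be affected, a subject must also fall in the band and meet every other component. If half did so (assumption), the expected number is 0.3 to 1.5 and the chance of at least one is 1 − 0.99^30 = 26% to 1 − 0.95^30 = 79%. A smaller share lowers both further.

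**The case against.** The strongest objection is that the fault rests on one digit in one table cell of a text read from PDF, and that this reading demonstrably damages tables elsewhere. The year 2 to 5 visit window, for example, appears in several different forms across the schedule tables. A misread digit cannot be excluded, so the source page should be checked first. It remains only a possibility: the rest of the row is intact, and as it stands the row contradicts itself.

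Second, Section 15.1.2 leaves detailed methods to a separate Statistical Analysis Plan, Section 13.2 leaves echo measurement to a core laboratory procedure, and the PPM entry cites VARC-2. Any of these may hold a usable limit. That is a reason not to conclude that grades would be picked once the values are seen, which a reader might infer. It does not repair the rule printed in the protocol.

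Third, the reach is easily overstated. A reader might infer that device success is undefined for every subject with BMI ≥ 30 in the band. It is not: operative death, malposition, a failed gradient or velocity criterion, or regurgitation of moderate grade or worse makes the subject a failure whatever the mismatch grade. A reader might also take 45% to 96% as the chance that the endpoint is affected. It is the chance of enrolling at least one subject with BMI ≥ 30 under an assumed prevalence.

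Fourth, the documents nowhere state that 0.70 is the intended limit. The direction of the row supports it but does not prove it.

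**Conclusion.** The point stands within narrow limits. As printed, the BMI ≥ 30 row double-grades 0.70 < EOAi ≤ 0.90. The PPM sentence cannot settle it because its limit is confined to BMI < 30, and the protocol gives no other mismatch limit. The protocol also does not say whether the sentence's velocity-coefficient condition applies to the table grades.

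The consequence is 3.3 percentage points of device success per affected subject, assuming all 30 planned subjects are evaluable. The number affected is unknown, is at most the number with BMI ≥ 30 and probably smaller, and may be zero.

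Nothing in the documents supports carrying this further. For device success and the other secondary endpoints Section 15.1.2 says: "No statistical tests will be conducted for the secondary endpoints, but evaluate by descriptive statistics". One-year mortality, its alpha and the sample size do not depend on this table. It is still more than a typographical matter, because the cell is a threshold in the definition of a named endpoint, and it is worth correcting because the correction is nearly free.

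**What to change.** 1. Check the cell against the source page and against the definition cited in the PPM entry.
2. Make the classes meet. Subject to that check, the row's own pattern supports moderate as 0.70 to 0.60, next to not significant as > 0.70.
3. Correct the BMI unit in the row to kg/m², as in Section 10.2.1.
4. Add one sentence to the device success entry: absence of mismatch means the not-significant class for the subject's BMI group, that is EOAi > 0.85 for BMI < 30 and, once confirmed, > 0.70 for BMI ≥ 30.
5. If device success has already been tabulated, report which cut-off was used and how many subjects with BMI ≥ 30 fell in the band.

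The cost is one number, one unit and one sentence in the glossary, with the matching line in the programming specification. No new data are needed.

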9.2 Secondary Endpoints

9.2.1 Secondary safety endpoints

- Composite endpoint: Post-procedure 30 days, 6 months, 1 year, and 2 to 5 years annually
 - Death and stroke
- Single endpoints: Post-procedure 30 days, 6 months, 1 year, and 2 to 5 years annually
 - Death (cardiovascular, non-cardiovascular)
 - MI (periprocedural, spontaneous)
 - Stroke (disabling, non-disabling)
 - Bleeding (life-threatening or disabling, severe, mild)
 - Vascular access site/access-related complications
 - Severe vascular complications
 - Conduction disorder/arrhythmia
 - Conduction disorder requiring new pacemaker implantation
 - Aortic valve re-intervention
 - Coronary obstruction
 - Endocarditis
 - Valve explants
 - Structural valve deterioration
 - Nonstructural valve dysfunction

Table 10-1: Permissible time windows for the tests/observations

Test/observation timing	Baseline ^{a)}	Procedure ^{b)}	Immediately after procedure	Post-procedural follow-up observation		
				Hospital discharge	30 days post-procedure	6 months post-procedure
Reference date (time)	-	Day 0	Up to 72 hours after exiting the operation room	7 days post-procedure or hospital discharge, whichever comes earlier	30 days post-procedure	182 days post-procedure
Permissible time window	Within 60 days pre-procedure	-	-	± 2 days	-7 days/+14 days	± 30 days

^{a)} The 12-lead ECG should be performed within 48 hours prior to entering the operation room, clinical laboratory tests within 14 days prior to the procedure, and coronary angiography and aortofemoral blood vessel evaluation (CT, MRI, or X-ray) within 90 days pre-procedure (see Section 10.2.1 "Baseline"). For the continued access registry, except cases that may be clinically valid, coronary angiography should be performed within 1 year prior to the study procedure.

^{b)} Cardiac catheter test at procedure should be performed immediately before and after the procedure.

Table 10-2: Permissible time windows for the tests/observations

Test/observation timing	Post-procedural follow-up observation				
	1 year post-procedure	2 years post-procedure	3 years post-procedure	4 years post-procedure	5 years post-procedure
Reference date	365 days post-procedure	730 days post-procedure	1095 days post-procedure	1460 days post-procedure	1825 days post-procedure
Permissible time window	± 30 days	± 45 days	± 45 days	± 45 days	± 45 days

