10.2 Tests/Observations

10.2.1 Baseline

For the baseline tests/observations, the following data will be collected from subject consent to before the study procedure. From the standpoint of protection of subjects, if any data are available on the tests performed within the permissible time windows specified in the protocol, the data obtained before informed consent and data used for screening may be used as baseline data.

- Informed consent
- Conformance to the inclusion/exclusion criteria
- Patient background
 - Demographic background
 - Sex, date of birth, and age (calculated from the date of birth)
 - Physical finding
 - Height, weight, body surface area (BSA), and BMI
 - BSA and BMI will be calculated from height and weight in the following formulas.
 - BSA = 0.007184 × Weight [kg]^{0.425} × Height [cm]^{0.725}
 - BMI = Weight [kg]/Height [m]²
 - Clinical background
 - Primary disease, risk factors (pre-procedural complication, past history, history of syncope not associated with atrioventricular block, number of hospitalization for AS in the past 6 months, and stroke in the past 12 months), type of dialysis (hemodialysis or peritoneal dialysis), the starting time of dialysis, duration of dialysis (to be calculated from the starting time of dialysis), and primary disease for introduction of dialysis
- Surgical risk assessment

After investigation/evaluation of surgical risks and risk score, evaluate patients who are not eligible for safe open surgical therapy as to whether or not the best therapy is treatment with EWJ-003.

 - STS score [<http://riskcalc.sts.org/stswebriskcalc/#/>]
 - Logistic EuroSCORE [<http://www.euroscore.org/calculd.html>]
 - EuroSCORE II [<http://www.euroscore.org/calc.html>]

* The results of risk score should be printed out and affixed to medical records, etc.
- NYHA classification of cardiac performance (see Section 30 "GLOSSARY")
- Canadian Cardiovascular Society (CCS) status of stable angina (see Section 30 "GLOSSARY")
- Neurological examination
 - National Institutes of Health Stroke Scale (NIHSS) (see Appendix 1)
 - Modified Rankin Scale (mRS) (see Appendix 2)

* Neurological assessment should be performed by a neurologist, neurosurgeon, or a physician

who is able to perform appropriate assessment.

- Blood pressure (systolic, diastolic)
- 12-lead ECG (to be performed within 48 hours prior to entering the operating room)
- Chest X-ray
- Head CT
- Six Minute Walk Test (see Appendix 3)

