13 EVALUATION BY THIRD-PARTY JUDGMENT ORGANIZATION

13.1 Clinical Event Adjudication Committee

To avoid bias among study sites and physicians, and to ensure consistent and objective evaluation, the major clinical events reported by the study sites will be assessed by Clinical Event Committee (CEC) that is independent from the study organization including the sponsor and study sites. The CEC consists of at least 1 member with expertise in this present disease area and study treatment, and at least 1 member with expertise in neurological disease area, and as shown below, performs review and adjudication of all death cases and cases with stroke occurred in all enrolled subjects in this clinical trial (including continued access registry) up to 1 year post-procedure. For CEC opening requirements and detailed activities and operating procedure, see "EWJ-003 Clinical Event Adjudication Procedure."

- Death

For all death cases reported by the study sites within 1 year post-procedure, the CEC will adjudicates the cause of death (cardiovascular or non-cardiovascular death) and the causal relationship to the study device and study procedure, in accordance with VARC-2 guideline⁵⁶¹ (see Section 30 "GLOSSARY").

- Stroke

For all stroke cases reported by the study sites within 1 year post-procedure, the CEC will adjudicates the events (disabling stroke or non-disabling stroke) and the causal relationship to the study device and study procedure, in accordance with VARC-2 guideline⁵⁶¹ (see Section 30 "GLOSSARY").

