mRS	
A commonly used international scale as the prognosis rating scale for daily activities of patients with stroke.
 
  
 0	No symptoms at all	
 
 1	No significant disability despite symptoms; able to carry out all usual duties and activities	
 
 2	Slight disability; unable to carry out all previous activities, but able to look after own affairs without assistance	
 
 3	Moderate disability; requiring some help, but able to walk without assistance	
 
 4	Moderately severe disability; unable to walk without assistance and unable to attend to own bodily needs without assistance	
 
 5	Severe disability; bedridden, incontinent and requiring constant nursing care and attention	
 
 6	Dead	
  
 
(see Appendix 2 "Modified Rankin Scale (mRS)")
	0	No symptoms at all	1	No significant disability despite symptoms; able to carry out all usual duties and activities	2	Slight disability; unable to carry out all previous activities, but able to look after own affairs without assistance	3	Moderate disability; requiring some help, but able to walk without assistance	4	Moderately severe disability; unable to walk without assistance and unable to attend to own bodily needs without assistance	5	Severe disability; bedridden, incontinent and requiring constant nursing care and attention	6	Dead	
0	No symptoms at all															
1	No significant disability despite symptoms; able to carry out all usual duties and activities															
2	Slight disability; unable to carry out all previous activities, but able to look after own affairs without assistance															
3	Moderate disability; requiring some help, but able to walk without assistance															
4	Moderately severe disability; unable to walk without assistance and unable to attend to own bodily needs without assistance															
5	Severe disability; bedridden, incontinent and requiring constant nursing care and attention															
6	Dead															

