Stroke/transient ischemic attack	
<Stroke/transient ischemic attack diagnostic criteria>
 
Acute onset of a local or general neurological disorder, with at least one of the followings: changes in the conscious level, hemiplegia, hemiparesis, numbness, sensory loss affecting one side of the body, dysphasia or aphasia, hemianopia, amaurosis fugax, and other neurological signs or symptoms consistent with stroke.
 
Stroke: Local or general neurological disorder sustains ≥ 24 hours, or even < 24 hours new hemorrhage or infarction is found by head neuroimaging, or a neurological disorder resulted in death.
 
Transient ischemic attack: Local or general neurological disorder sustains < 24 hours, with no new hemorrhage or infarction by head neuroimaging.
 
As for clinical findings, the absence of causes other than stroke that can be easily identified (brain tumor, trauma, infection, hypoglycemia, peripheral lesion, influence of drug, etc.) must have been determined by a neurologist or together with a neurologist*. Definitive diagnosis should be made by at least one of the followings:
 
 • Diagnosis by a neurologist or neurosurgeon • Head neuroimaging (CT scan or brain MRI); however stroke may be diagnosed only by the clinical findings 
* Do not report non-local encephalopathy as stroke, unless findings of cerebral infarction are present based on the head neuroimaging (CT scan or brain MRI).
 
<Stroke classification>
 
Ischemic: Acute angiopathy at the local brain, spinal cord, or retina associated with infarction in the central nervous system tissues
 
Hemorrhagic: Acute angiopathy at the local or general brain or spinal cord associated with hemorrhage in the cerebral parenchyma, cerebral ventricle, or
	VARC-2												

Term	Definition	Reference/rationale
	
subarachnoid
 
If the information is inadequate for determining ischemic or hemorrhagic, classify as cause unknown.
 
<Definition of stroke> Stroke is classified into disabling or non-disabling.
 
 • Disabling stroke At 90 days after the onset of a stroke, $mRS \geq 2$, and exacerbation ≥ 1 in the mRS from before the onset. • Non-disabling stroke At 90 days after the onset of a stroke, $mRS < 2$, and no exacerbation ≥ 1 in the mRS from before the onset. 	

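### The disabling and non-disabling stroke rules leave some strokes in neither class, and the split is listed to year 5 although mRS collection and committee classification stop at strokes within 1 year

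*Combined protocol and SAP*

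**What the plan says.** The stroke entry in the Section 30 glossary sets up two classes and no third: "Stroke is classified into disabling or non-disabling". Disabling requires a 90-day mRS of 2 or more together with worsening of at least 1 point from before the onset. Non-disabling requires a 90-day mRS below 2 "and no exacerbation" of that size. Both rules are conjunctions.

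Section 13.1 has the event committee apply the classification: "For all stroke cases reported by the study sites within 1 year post-procedure, the CEC will adjudicates the events (disabling stroke or non-disabling stroke"), following VARC-2 and pointing to the glossary. Its remit is "cases with stroke occurred in all enrolled subjects in this clinical trial (including continued access registry) up to 1 year post-procedure".

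Section 9.2.1 lists stroke, split into disabling and non-disabling, under this heading: "Single endpoints: Post-procedure 30 days, 6 months, 1 year, and 2 to 5 years annually".

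**The concern.** The opposite of 'A and B' is 'not A or not B'. A non-disabling rule that keeps 'and' is narrower than the complement of the disabling rule, so some strokes belong to neither class. There are two such patterns.

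- **mRS 0 before the stroke and 1 at 90 days.** The glossary's own scale describes grade 1 as "No significant disability despite symptoms; able to carry out all usual duties and activities", yet the non-disabling rule rejects this stroke because the score worsened by 1.
- **90-day mRS of 2 or more with no worsening.** This can occur because patients may enter with existing disability. Exclusion 17 bars only recent events ("Patient has had a cerebrovascular accident or transient ischemic attack within 6 months prior to the study procedure") and exempts those associated with AS. Section 10.2.1 records further history ("and stroke in the past 12 months"). No criterion limits baseline mRS.

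An adjudicator who meets either pattern must leave the stroke unclassified or apply an unwritten rule, and the two counts need not add up to all strokes. Under Section 18.3 the report on the 1-year data goes into the approval application, so the split should be reproducible from the written rule.

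The second problem is one of timing. The split is promised to year 5, but the data and the classification that produce it are specified only for strokes in the first year.

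**Working it through.** **1. Coverage of the two rules.** The plan states no figure here to reproduce, so the rules were enumerated. Let a be the pre-stroke mRS (0 to 5) and b the 90-day mRS (0 to 6, where 6 is death), using the glossary scale. This gives 6 × 7 = 42 pairs.

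- Disabling: b ≥ 2 and b − a ≥ 1
- Non-disabling as written: b < 2 and not (b − a ≥ 1)

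| a | disabling (b) | non-disabling (b) | neither (b) |
|---|---|---|---|
| 0 | 2–6 (5) | 0 (1) | 1 (1) |
| 1 | 2–6 (5) | 0, 1 (2) | none |
| 2 | 3–6 (4) | 0, 1 (2) | 2 (1) |
| 3 | 4–6 (3) | 0, 1 (2) | 2, 3 (2) |
| 4 | 5–6 (2) | 0, 1 (2) | 2, 3, 4 (3) |
| 5 | 6 (1) | 0, 1 (2) | 2, 3, 4, 5 (4) |
| Total | 20 | 11 | 11 |

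No pair meets both rules. Six of the 11 unclassified pairs need the score to improve after the stroke. Restricting to b ≥ a leaves 7 + 6 + 5 + 4 + 3 + 2 = 27 pairs:

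- 20 are disabling.
- 2 are non-disabling (0→0 and 1→1).
- 5 are neither (0→1, 2→2, 3→3, 4→4 and 5→5).

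**2. The same count with 'or'.** If non-disabling is b < 2 or not (b − a ≥ 1), the 11 unclassified pairs join the 11 non-disabling ones. The result is 20 disabling and 22 non-disabling, with none in neither class and none in both. For the 27 unchanged-or-worse pairs it is 20 and 7. The disabling count does not move.

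**3. Strokes after year 1.** Section 9.2.1 requires the split at years 2 to 5. The provisions that would supply it read as follows.

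| Place | What it provides |
|---|---|
| 10.2.7 | Last scheduled visit list for the analysis set with the post-stroke mRS instruction (1 year) |
| 10.2.8, and 10.3.8 for the registry | No mRS among the year 2–5 items |
| 10.2.9 and 10.2.10 (registry through 10.3.9) | Post-stroke mRS only for a stroke within 1 year |
| 13.1 | Committee source documents, mRS included, and classification only up to 1 year |

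These places agree with one another. The gap lies between them and the endpoint list.

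**4. Scale, for illustration only.** The documents give no stroke rate for this device in dialysis patients and none for years 2 to 5. The rates assumed here are 1 of 24 at 30 days in the dialysis series (Section 1.2.2.2), and 4.3% and 5.4% at 1 year in the two larger trials of this device, which excluded dialysis patients (Section 1.2.2.1).

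- 30 analysis-set subjects: 30/24 = 1.25; 30 × 0.043 = 1.29; 30 × 0.054 = 1.62 strokes of any kind.
- 80 subjects, adding the registry maximum of 50 (Section 4.4): 80/24 = 3.33; 80 × 0.043 = 3.44; 80 × 0.054 = 4.32.

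The second line indicates only the committee's caseload, because Section 15.3 analyses the registry separately. Only some of these strokes would fall in the gap.

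**The case against.** The best defence is that the intent is plain. The glossary announces two classes and the disabling rule is unambiguous, so a sensible adjudicator would call everything else non-disabling. That is probably what was meant, but it contradicts the non-disabling rule as written, which excludes a 0→1 stroke. The VARC-2 reference and the committee's own procedure may contain a workable rule. Neither is in the supplied documents, so it cannot be assumed that they repair the wording, nor can it be asserted that the counts will in fact fail to add up.

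On strokes after year 1, the post-stroke mRS footnote to Tables 10-3 and 10-4 carries no time limit. It is attached to a row that appears to be marked no later than 1 year, and it names no one to classify later strokes. The schedule tables are damaged in extraction, so the point rests on the section text in 10.2.7 to 10.2.10, 10.3.8, 10.3.9 and 13.1. Later strokes are still collected as adverse events, so they are not lost; only their class is.

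It is also fair to say that the stakes are low. Section 15.1.2 makes the secondary endpoints descriptive, the expected events are few, and counts of score pairs say nothing about how often each pair occurs. All of this stands and limits the weight of the point. With so few strokes, though, one unclassified case would visibly change the reported split.

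**Conclusion.** The concern holds on both parts. Read literally, the two rules leave 11 of 42 score pairs in neither class, or 5 of 27 if the score does not improve after the stroke. For new strokes after year 1, the listed split has no protocol-specified mRS and no classifier behind it. The first part follows from the glossary wording alone. The second follows from the visit lists and the committee's remit. How many patients would be affected is unknown; on the assumed rates, about one or two strokes of any kind would be expected in the 30 subjects.

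The disabling count up to year 1 is unaffected wherever a 90-day mRS exists, as are all-stroke counts, the death-and-stroke composite and the primary mortality endpoint. This should be corrected, but it does not threaten the trial's main conclusion.

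**What to change.** **Glossary.** Define non-disabling stroke as a 90-day mRS below 2, or no worsening of 1 point or more from before the onset. This is a one-word change that needs no new data for strokes up to 1 year. Align the event committee's procedure with it, and recheck any stroke already adjudicated as neither class or classified by an ad hoc rule. Section 27 shows that analysis-set enrolment has ended, so some strokes may already have been classified; on the illustration above this would be a handful of cases at most.

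**After year 1.** Choose one of two options:

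- Limit the disabling/non-disabling split in Section 9.2.1 and the synopsis to strokes within 1 year, and report all stroke thereafter. This costs nothing further.
- Extend the stroke-triggered mRS through year 5 (Sections 10.2.8 to 10.2.10 and 10.3.8) and name who classifies these strokes. This adds one stroke-triggered mRS assessment per late stroke and a named classifier.

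These are changes to protocol text, so they need a revision with IRB approval under Section 24.3. Sample size and the primary analysis do not change.
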